6.3 Control of Bias and Confounding

There will be no predilection towards race, ethnicity, sex or sexual orientation. Individuals included in this study will have limited recruit/selection biased. Because the study is focused on physical functionality of patients it will be isolating those patients having a hindfoot fusion procedure and will be recruited from the Foot & Ankle Institute at Western Pennsylvania Hospital, Forbes Regional Hospital, Jefferson Regional Hospital, Bethel Park Surgery Center, and Monroeville Surgery.

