The subjects will be identified/recruited during clinic hours as patients requiring an elective or traumatic foot and ankle surgery. During the clinic hours the primary investigator and/or the co-investigator will obtain full consent from the patient. We will recruit a minimum of 115 participants into each of two study arms, an immediate weight-bearing arm and a non-weight-bearing arm, so 230 participants will be included. Patients will be eligible if they are undergoing elective or traumatic foot and ankle surgery. Exclusion criteria will include any patient less than 18 years of age & over 89, history of foot or ankle surgery on the surgical limb, any degree of diagnosed peripheral neuropathy or peripheral vascular disease, infection, and/or unwillingness to participate at random in one of the two study arms.

Study Interventions and Measures:

We will be assessing the difference in two groups; immediate protected weight-bearing in a CAM walking boot vs strict non-weight-bearing for 6 weeks following foot and ankle surgery. Monitoring will be done by way of clinical follow-up, serial radiographs and/or other appropriate imaging modalities, and patient reported outcomes by way of AOFAS and SF-36 surveys.

Surgical procedures performed on patients included in the study will vary, as will the outcome measures for each procedure. Osseous fusions, including both elective joint fusions and bone healing following trauma, will be assessed by both clinical and radiographic evaluation. Soft tissue procedures, including elective stabilization and traumatic soft tissue repairs, will be assessed clinically and with imaging modalities

deemed appropriate. Complications during the perioperative and post-operative periods, such as non-union, infection, etc. will be included in the outcomes. All participants will also complete AOFAS and SF-36 surveys in the pre-operative and post-operative periods. We will also include return to work, activity, sport, etc. where appropriate.

Study Phase	Screening	Surgery	Post-op 2-3 w	Post-op 6-8 w	Post-op 3 m	Post-op 6 m	Post-op 1 yr	Post-op 2 yr	Unscheduled Visits
Visit Number	1		2	3	4	5	6	7	
Informed									
Informed Consent/Assent	x								
Review Inclusion/Exclusion									
Criteria	х								
Randomization	x								
Demographics/PMH	x								
Physical Examination	x		x	x	x	x	x	x	x
Adverse Event Assessment			x	x	x	x	x	x	x
Radiographs/Imagining	х		x	x	x	x	x	x	x
Complete AOFAS/SF- 36 survey	x			x	x		x	x	

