1 BACKGROUND INFORMATION AND RATIONALE

1.1 Introduction

There is an ongoing debate within the surgical community as to whether it is best to keep patients who have undergone foot and ankle surgery non-weight-bearing (NWB) for an extended period of time versus allowing them to bear weight early, or on occasion, immediately. The standard for many foot and ankle procedures involving fusion of bone and repair of ligaments and tendons has been to keep the patient completely NWB for 6-8 weeks, or the approximate time it takes for bone and tendon to heal, on average. This standard has been challenged in recent years, with more surgeons allowing their patients to bear weight earlier than previously considered safe. Our aim is to assess if immediate weightbearing following any foot and ankle procedure is equally as safe and effective as an extended course of NWB in patients meeting our inclusion criteria.

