3.3 Study Population

3.3.1 Inclusion Criteria

- 1) Males or females age 18 to 89 years
- 2) Undergoing foot and ankle surgery
- 3) Must be able to read and understand English and consent for themselves

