6.2 Secondary Endpoints

The secondary outcome measures are the frequency of complications during the perioperative and post-operative periods, osseous healing as assessed by both clinical and radiographic evaluation, and healing outcomes of soft tissue procedures. These results will be analyzed at the end of the follow-up period.

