APPENDIX

Append relevant information.

- I. DATA COLLECTION FORMS
 - a. See attached
- II. APPENDIX
 - a. Questionnaires

DATE:		VISIT: Pre-Op F/U: #1 #2 #3 #4 #5
PTID#		DATE OF SURGERY:
STUDY GROUP:	Immediate Weightbearing	Non-Weightbearing
AGE	GENDER	R M F BMI
HISTORY OF SM	IOKING None Previou	us Current If yes, how many packs/day?
HISTORY OF DI	ABETES Yes No	If yes, last A1c value?
	S:	
RADIOGRAPHIC	C/ADVANCED IMAGING FINDING	: Pre-Op #1 #2 #3 #4 #5
XRAY:		
CT:		
MRI:		Procedure(s):
MRI: Pre-Op:	VAS:	Procedure(s): 1 st MPJ fusion DMO 1 st TMT fusion
MRI: Pre-Op:		Procedure(s):
MRI: Pre-Op: AOFAS: Follow-up Visit	VAS: #2 (6-8 weeks Post-Op):	Procedure(s): 1 st MPJ fusion DMO 1 st TMT fusion
MRI: Pre-Op: AOFAS: Follow-up Visit	VAS:	Procedure(s): 1 st MPJ fusion DMO 1 st TMT fusion LisFranc ORIF Midfoot fusion 5 th met ORIF
MRI: Pre-Op: AOFAS: Follow-up Visit	VAS: #2 (6-8 weeks Post-Op):	Procedure(s): 1 st MPJ fusion DMO 1 st TMT fusion LisFranc ORIF Midfoot fusion 5 th met ORIF TNJ fusion STJ fusion PCDO PMGL
MRI: Pre-Op: AOFAS: Follow-up Visit AOFAS:	VAS: #2 (6-8 weeks Post-Op):	Procedure(s): 1 st MPJ fusion DMO 1 st TMT fusion LisFranc ORIF Midfoot fusion 5 th met ORIF TNJ fusion STJ fusion PCDO PMGL Achilles repair FHL transfer FDL transfer
MRI: Pre-Op: AOFAS: Follow-up Visit AOFAS: Follow-up Visit	VAS: #2 (6-8 weeks Post-Op): VAS:	Procedure(s): 1 st MPJ fusion DMO 1 st TMT fusion LisFranc ORIF Midfoot fusion 5 th met ORIF TNJ fusion STJ fusion PCDO PMGL Achilles repair FHL transfer FDL transfer Peroneal repair ATT transfer PTT repair
MRI: Pre-Op: AOFAS: Follow-up Visit AOFAS: Follow-up Visit	VAS: #2 (6-8 weeks Post-Op): VAS: #4 (12 months Post-Op):	Procedure(s): 1 st MPJ fusion DMO 1 st TMT fusion LisFranc ORIF Midfoot fusion 5 th met ORIF TNJ fusion STJ fusion PCDO PMGL Achilles repair FHL transfer FDL transfer Peroneal repair ATT transfer PTT repair Fibula ORIF Tibia ORIF Bimal ORIF
MRI: Pre-OD: AOFAS: Follow-up Visit AOFAS: Follow-up Visit	VAS: #2 (6-8 weeks Post-Op): VAS: #4 (12 months Post-Op):	Procedure(s): 1 st MPJ fusion DMO 1 st TMT fusion LisFranc ORIF Midfoot fusion 5 th met ORIF TNJ fusion STJ fusion PCDO PMGL Achilles repair FHL transfer FDL transfer Peroneal repair ATT transfer PTT repair Fibula ORIF Tibia ORIF Bimal ORIF Ankle fusion TAR

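### Section 6.3 and the SF-36 form describe a hindfoot-fusion study, while eligibility, endpoints and the pooled primary analysis cover any foot and ankle surgery

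*Combined protocol and SAP*

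**What the plan says.** Two places describe a hindfoot-fusion study:

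- Section 6.3 (Control of Bias and Confounding) says that, because the focus is physical functionality, "it will be isolating those patients having a hindfoot fusion procedure".
- The SF-36 form in the Appendix opens by asking patients for views on their health in relation to their hindfoot fusion.

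The rest of the plan describes a broad population:

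- Abstract: "Patients will be eligible if they are undergoing elective or traumatic foot and ankle surgery". It adds: "Surgical procedures performed on patients included in the study will vary, as will the outcome measures for each procedure".
- Section 1.1: the aim concerns "immediate weightbearing following any foot and ankle procedure".
- Section 3.3.1: the only criterion about the operation is "Undergoing foot and ankle surgery". No exclusion in 3.3.2 limits the type of procedure.
- Section 6.1: the SF-36 is a primary outcome, tied to the patient's ankle or foot.
- Section 6.2: the secondary outcomes include "healing outcomes of soft tissue procedures".
- Section 6.4.1, last paragraph: the primary analysis compares the two arms across the various procedures, and single-procedure analyses are exploratory.
- Appendix, data collection form: the procedure list includes, for example, "Achilles repair FHL transfer FDL transfer".

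Section 6.4.1 adjusts SF-36 and AOFAS scores for age, gender, BMI and diabetes. Procedure is not among the covariates.

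**The concern.** Hindfoot fusion is a subset of foot and ankle surgery. A patient with an Achilles repair, a first MPJ fusion or a fibula fixation is eligible under 3.3.1 but is not a patient of the kind 6.3 describes. Both statements cannot hold, and no sub-study or subset is defined that would let them.

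Two things are at stake. First, the section headed as the control of bias and confounding names a restriction that the trial does not apply, so its account of the study population is wrong. Second, the wording has reached a primary instrument. An eligible patient without a hindfoot fusion is asked to rate health in relation to an operation that he or she did not have. Such a patient may substitute the actual operation, answer generally, or leave items blank, and the plan does not say how the instruction should then be read. Both arms receive the same form, so this does not by itself imply bias towards either arm. It does make the content of a primary outcome uncertain.

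**Working it through.** **1. Can the texts be reconciled?** Each broad statement was read against 6.3.

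- 3.3.1 and 3.3.2 set no limit on procedure, so eligibility is wider than 6.3.
- The abstract admits elective and trauma surgery, both osseous and soft tissue. Soft tissue repair is not fusion.
- 6.2 makes soft tissue healing a secondary outcome, which would have little purpose if only hindfoot fusions enrolled.
- 6.4.1 expects small numbers per procedure and pools them, which presupposes several procedures.
- 6.1 ties the SF-36 to the ankle or foot, while the form ties it to hindfoot fusion.

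No reading satisfies all of these together with 6.3.

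**2. Count of procedures on the data form.** Taken row by row, the list gives 3 + 3 + 4 + 3 + 3 + 3 + 2 = 21 entries. Hindfoot fusions are TNJ and STJ fusion, so 2; with ankle fusion, 3.

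- Inside 6.3: 2/21 = 9.5%, or 3/21 = 14.3%.
- Outside 6.3: 21 − 2 = 19 or 21 − 3 = 18, that is 90.5% or 85.7%.

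These are shares of form entries. The field allows more than one procedure per patient, and no expected case mix is given.

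**3. Exposure of the primary instrument.** Table 1 schedules the surveys at screening, 6–8 weeks, 3 months, 1 year and 2 years. That is five administrations, in agreement with 7.5. The wording problem applies at each.

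**4. Does the sample size depend on the population label?** Inputs from 6.5: d = 0.40, two-sided alpha 0.05, power 80%, 100 evaluable per group, plus 15 per group for loss.

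- Normal approximation: n = 2(1.960 + 0.842)²/0.40² = 98.1, rounded up to 99 per group.
- Noncentral t: n = 99.08, rounded up to 100 per group. Power with 100 per group is 80.4%.
- Allowance for loss: 100 + 15 = 115 per group, and 2 × 115 = 230.

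The stated figures reproduce. They rest on a standardised effect, so they do not change when 6.3 is reworded.

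**5. Cost of a procedure-class covariate.** Two binary factors (osseous or soft tissue; elective or traumatic) use 2 degrees of freedom. Take a comparison at one visit with 200 evaluable patients, and assume one degree of freedom for each of the four covariates already planned. The residual degrees of freedom go from 200 − 2 − 4 = 194 to 192.

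**The case against.** The strongest reply is that this is one outlying sentence, probably carried over from another protocol, plus a form instruction. The carry-over is an inference that the documents do not state, but the weight of the text favours it. Several stronger readings fail for this reason:

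- *Sites would recruit different populations.* A reader might infer this from 6.3. But 3.3 governs enrolment, says that subjects who do not meet all the criteria may not be enrolled, and is unambiguous. Section 6.3 is not an eligibility section.
- *Readers of section 6 would take the result to apply to hindfoot fusion only.* Section 6 itself points the other way: its opening purpose and hypothesis, 6.2 and the end of 6.4.1 all use the broad population.
- *About nine in ten patients fall outside 6.3.* The 18 or 19 of 21 counts form entries. The documents do not support turning it into a share of patients.
- *The trial is underpowered for its population.* If a hindfoot-only result were wanted from mixed enrolment, power at d = 0.40 would depend on a share that the documents do not give: about 14% if one in ten patients had hindfoot fusion, 28% at one in four, 51% at one in two. But the plan treats single-procedure analyses as exploratory and makes no such claim.

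It can also be said that 6.3 gives physical functionality as its reason and never mentions case mix. A procedure covariate would then be a new analysis choice, given that 6.4.1 already chose a pooled comparison and plans a regression on surgical characteristics. This stands in part: the contradiction can be removed without the covariate. But adjusting for class keeps the pooled comparison. Section 6.4.1 rules out adjustment for center and says nothing similar about procedure. The planned regression asks which characteristics go with higher scores and is not described as an adjusted comparison of the arms.

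None of these replies removes the conflict between 6.3 and 3.3.1, or between the SF-36 form and 6.1.

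**Conclusion.** The point holds as an internal inconsistency that should be corrected. Section 6.3 states a restriction that the trial does not apply, and a primary-outcome form is worded for an operation that eligible patients need not have had.

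Its extent is two places (6.3 and the SF-36 form), five administrations of that form, and 18 or 19 of 21 listed procedures outside the 6.3 description. The effect on SF-36 scores cannot be sized, because neither the case mix nor the way patients would answer the instruction is given. The sample size and power as stated do not change.

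The conclusion assumes that 3.3 is the intended population, as most of the document indicates. The covariate rests on a separate ground. The planned adjustment omits procedure, and allocation in 3.1 is one coin flip followed by alternation, with recruitment at the surgeons' discretion (7.1.1, 7.4). Balance of case mix between arms therefore should not be taken for granted. Whether that allocation method is adequate is a different question.

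**What to change.** 1. In 6.3, replace the hindfoot-fusion sentence with the population of 3.3.
2. On the SF-36 form, change the opening instruction so that it agrees with 6.1 and refers to the patient's foot or ankle. Record the version date. If any forms have already been completed on the present wording, note which ones.
3. In 6.4.1, add a pre-specified procedure class to age, gender, BMI and diabetes. The abstract already supplies usable classes: osseous or soft tissue, and elective or traumatic. State in advance how a patient with procedures in more than one class is assigned. Keep the pooled comparison as primary and the single-procedure analyses as exploratory.

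The cost is a protocol wording change, one form revision with IRB submission, and about 2 degrees of freedom. Procedure is already recorded on the data form, so no new data are needed. Recruitment and the total of 230 stay as they are, provided that sites follow 3.3. In return, the stated population is consistent, the primary instrument fits every eligible patient, and the comparison gains some protection against case-mix imbalance, and precision to the extent that procedure class predicts the scores.

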6.4 Statistical Methods

6.4.1 Analysis of Primary Outcome of Interest

All analysis will begin with assessment of the normality of continuous variables using the Kolmogorov-Smirnov test. Normally distributed continuous variables will be reported as means and standard deviations; non-normally distributed data as median and interguartile range. Categorical data will be reported as counts and percentages. The Student's t-test will be used to compare continuous demographic and clinical data between the immediate weight-bearing and non-weight-bearing groups. The chi-square test or Fisher's exact test will be used to compare categorical data between groups. Cronbach's alpha will be used to measure reliability, or internal consistency, of both the Medical Outcomes Study 36-Item Short Form Health Survey (SF-36) and the AOFAS Ankle-Hindfoot Scale survey (AOFAS). Spearman's rank correlation coefficient will be used to assess the relationship between the physical and mental component scores and the eight subdomain scores from the SF-36 and the pain, function and alignment scores of the AOFAS. SF-36 scores and AOFAS scores will be adjusted for patient age, gender, BMI and presence of diabetes mellitus. Nonparametric tests will be used when data breaks the normality assumption. A value of p<.05 on twotailed testing will be considered statistically significant. Statistical analysis will be performed using IBM-SPSS Statistics, version 24.0 (IBM-SPSS Inc., Armonk, NY). Using one-way repeated measures analysis of variance (ANOVA), differences over time in radiographic and advanced imaging parameters will be assessed separately for the immediate weight-bearing and non-weight-bearing groups. Two-way repeated measures ANOVA will be used to assess differences over time in these parameters between the two groups. Tukey's test or Dunn's procedure will be used for post-hoc pairwise comparisons, as indicated.

Descriptive statistics on the physical and mental component scores and the eight subdomain scores from the SF-36 will be reported for the immediate weight-bearing and non-weight bearing groups. In order to examine differences in SF-36 scores within each group over time, a one-way repeated measures ANOVA will be conducted to determine if the SF-36 scores are significantly different between visits (e.g., screening, post-operative at 6-8 weeks, post-operative at 12 months, and post- operative at 24 months). A two-way repeated measures ANOVA will be conducted to determine if the SF-36 scores are significantly be conducted to determine if the SF-36 scores are significantly be conducted to determine if the SF-36 scores are significantly be conducted to determine if the SF-36 scores are significantly be conducted to determine if the SF-36 scores are significantly be conducted to determine if the SF-36 scores are significantly be conducted to determine if the SF-36 scores are significantly be conducted to determine if the SF-36 scores are significantly different between the two groups for these same visits. Post-hoc pairwise comparisons using Tukey's test or Dunn's procedure will be performed, as indicated.

Descriptive statistics on the pain, function and alignment component scores from the AOFAS will be reported for the immediate weight-bearing and non-weight bearing groups. In order to examine differences in AOFAS scores within each group over time, a one-way repeated measures ANOVA will be conducted to determine if the AOFAS scores are significantly different between visits (e.g., screening, post-operative at 6 – 8 weeks, post-operative at 12 months, and post-operative at 24 months). A two-way repeated measures ANOVA will be conducted to determine if the AOFAS scores are significantly different between visits. Post-hoc pairwise comparisons using Tukey's test or Dunn's procedure will be performed, as indicated.

The chi-square test will be used to examine the frequency of complications during the perioperative and post-operative periods, osseous healing as assessed by both clinical and radiographic evaluation and frequency of soft tissue procedures between the immediate weight-bearing and non-weight bearing groups.

Logistic regression analysis will be performed to assess which patient characteristics and surgical characteristics are associated with higher SF-36 scores and AOFAS scores.

Due to the potential small sample sizes associated with the various orthopaedic procedures included in this study, the primary analysis will focus on the comparison of the immediate weight-bearing and non-weight bearing groups. Any analyses associated with an individual orthopaedic procedure will be considered exploratory. Finally, the data will not be adjusted for the center where the procedure was performed.

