4 STUDY PROCEDURES

4.1 Screening Visit

Below is a list of all of the procedures to be performed at each visit.

- Informed Consent
- Physical Exam
- Radiographic/Advanced Imaging
- Medical Record Review
 - Review of the medical record will include reviewing the past medical and surgical history, laboratory values, and most recent visits to other health care providers in the standard fashion of any office or inpatient encounter
- Surgical procedure discussed and operative consent
- Pre-operative AOFAS and SF-36 surveys completed

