6.5 Sample Size and Power

The study power calculation is based on the primary endpoints.

Assuming the American Orthopaedic Foot and Ankle Society (AOFAS) Ankle-Hindfoot Scale score and the SF-36 Health Survey Score (as it pertains to the patient's foot/ankle) are normally distributed in the immediate weight-bearing and non-weight-bearing groups and using an independent-samples t-test with a .05 two-sided significance level, and (absent any prior study results) assuming a "medium" effect size of Cohen's d = 0.40, 200 evaluable patients (100 patients in each group) would give you a power of 80% to detect a true difference in means on the questionnaires, if present. Fifteen patients will be added to each group for the potential of loss to follow-up. Final sample size is 230 patients (115 patients in each group). Sample size was calculated using an a-priori sample size calculator for Student t-tests (2017) available from http://www.danielsoper.com.

¹ "Effect size" is a statistical expression of the magnitude of the difference between two groups (Portney and Watkins, 2000). The standardized mean effect, one type of effect size, expresses the mean difference between two groups in standard deviation units. This is

typically reported as Cohen's "d." Interpretation of effect size depends on the research question. Cohen (1988) defines his effect sizes as: 8 = large (8/10 of a standard deviation unit). 5 = moderate (1/2 of a standard deviation). 2 = small (1/5 of a standard deviation). I would recommend using the "medium" effect size for your project. A medium effect size can range from 0.3 to 0.5.

SAFETY MANAGEMENT

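### The pre-operative AOFAS and SF-36 scores are collected but not used as a covariate, and screening is listed as an outcome visit with no arm term named, so precision is lost on every reading

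*Combined protocol and SAP*

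**What the plan says.** Section 6.1 makes the AOFAS and SF-36 scores the primary outcomes. Both are obtained before surgery; section 4.1 lists "Pre-operative AOFAS and SF-36 surveys completed" among the screening procedures.

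Section 6.4.1 sets the adjustment: "SF-36 scores and AOFAS scores will be adjusted for patient age, gender, BMI and presence of diabetes mellitus". The pre-operative score is not among these variables, and no other section adds it or plans a change-score analysis.

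The same section first plans a one-way repeated-measures ANOVA within each arm, to see whether SF-36 scores are "significantly different between visits (e.g., screening, post-operative at 6-8 weeks, post-operative at 12 months" and at 24 months. A two-way repeated-measures ANOVA then compares the arms over those same visits, so screening is an outcome level in the arm comparison. The AOFAS paragraph has the same visit list, but its two-way sentence speaks only of differences between visits and does not mention the arms. Section 6.4.1 closes by saying that the primary analysis focuses on comparing the two arms. It does not say whether the arm effect is the group main effect, the group-by-visit interaction or a contrast at a particular visit.

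Section 6.5 sizes the trial "using an independent-samples t-test with a .05 two-sided significance level", with no baseline term and no named time point.

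**The concern.** A pre-operative score of the same instrument is often among the better predictors of the post-operative score. Used as a covariate, it removes the part of the between-patient variation that it explains. Here it is measured on every patient and then not used in that way.

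Putting screening among the outcome visits has a second consequence that depends on the reading. Weight-bearing status cannot affect a score taken before surgery. A term that averages the arm difference over all visits therefore averages in a difference whose expected value is zero, together with whatever chance difference the arms show at screening. A term that looks at change over visits, or at one visit, does not do this. Because the plan names no term, the reader cannot tell which applies, and the choice stays open until the data are in hand.

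**Working it through.** **Inputs.** From section 6.5: two-sided 0.05, d = 0.40 (SD = 1), 100 evaluable patients per arm. From section 6.4.1: four listed visits, of which three are post-operative. Assumed, because the documents give no value: correlation r between any two visits of 0.3 / 0.5 / 0.6, equal variances and correlations at all visits, and no expected arm difference at screening. The gain from age, gender, BMI and diabetes is not counted; if they explain part of what the baseline explains, r should be read as the correlation left after them.

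**1. The plan's own figure.** Noncentral t with 198 df and noncentrality 0.40 × √(100/2) = 2.83 gives 80.4% power. With 99 per arm it gives 79.97%, so 100 is the smallest adequate number. The stated 80% reproduces, and 100 + 15 = 115 per arm matches the final size.

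**2. One post-operative visit, baseline as covariate.** The residual variance is 1 − r², so the standardised effect is 0.40 / √(1 − r²).

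| r | 1 − r² | effect | power |
|---|---|---|---|
| no covariate | 1 | 0.400 | 80.4% |
| 0.3 | 0.91 | 0.419 | 83.9% |
| 0.5 | 0.75 | 0.462 | 90.1% |
| 0.6 | 0.64 | 0.500 | 94.0% |

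Equivalently, about 91 / 75 / 64 patients per arm do the work of 100.

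**3. Effect of 0.40 at all three post-operative visits.**

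- *Group main effect, screening included.* Expected difference (0 + 0.40 + 0.40 + 0.40)/4 = 0.30. The variance of a four-visit mean is (1 + 3r)/4.
- *Group-by-visit interaction, 3 df.* The squared deviations of (0, 0.40, 0.40, 0.40) from 0.30 sum to 0.09 + 3 × 0.01 = 0.12. Noncentrality is 50 × 0.12/(1 − r) = 8.57 / 12.0 / 15.0 on 3 and 594 df.
- *Post-operative mean, no baseline.* Difference 0.40, variance (1 + 2r)/3.
- *Post-operative mean, baseline as covariate.* Difference 0.40, variance (1 + 2r)/3 − r².

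| analysis | r = 0.3 | r = 0.5 | r = 0.6 |
|---|---|---|---|
| main effect with screening | 86.5% | 76.1% | 71.3% |
| interaction | 68.4% | 83.8% | 91.5% |
| post-operative mean, unadjusted | 97.1% | 93.2% | 90.8% |
| post-operative mean, baseline-adjusted | 98.8% | 99.2% | 99.6% |

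**4. Dilution.** A simulation of 4,000 trials at r = 0.5 gave a mean main effect of 0.299 and a mean difference at one post-operative visit of 0.398. The main effect is diluted and the per-visit contrast is not. The visit list is given only as an example, and Table 1 and section 4.3 also schedule the surveys at 3 months. With that visit added, the main effect is 4 × 0.40/5 = 0.32.

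**The case against.** The strongest reply is that a two-way repeated-measures ANOVA yields a group-by-visit term. With a pre-treatment visit in the model, that is the usual term for an arm difference in change. It is not diluted by screening, and it uses each patient's baseline implicitly. Post-hoc contrasts at single visits are not diluted either. This stands: a reader might infer that the plan's arm effect is biased toward zero, but the documents do not support that, because they never say the main effect is the one to be used. The SF-36 wording leans that way; it does not settle it.

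A second tempting reading takes an effect confined to 6-8 weeks. The main effect is then 0.40/4 = 0.10, with power of 17.5 / 14.5 / 13.4%, against 83.9 / 90.1 / 94.0% for a baseline-adjusted contrast at that visit. This gap should not be charged to the screening visit. Without screening, the unadjusted post-operative mean, 0.40/3 = 0.133, still has only 25.0 / 21.0 / 19.5%; most of the loss comes from averaging over later visits with no effect. The interaction, whose squared deviations again sum to 0.12, keeps 68.4 / 83.8 / 91.5%.

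Third, omitting the baseline does not bias a post-operative contrast between properly randomised arms or inflate its type I error, and the gain depends on an unstated correlation. Trauma patients complete the pre-operative survey after injury, so their correlation may be low; at r = 0.3 the single-visit gain is only 80.4% to 83.9%. This also stands. It limits the size of the point but does not remove it: over the range examined, the baseline-adjusted analysis has the highest power in each comparison.

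**Conclusion.** The point holds as a loss of precision and an unnamed arm term. At a single visit the baseline covariate is worth 3.5 to 13.6 percentage points of power (83.9 − 80.4; 94.0 − 80.4) for r from 0.3 to 0.6. For a constant post-operative effect, the adjusted post-operative mean has at least 98.8% power, while the terms of the planned ANOVA range from 68.4% to 91.5%.

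Dilution is conditional. It arises only if the group main effect is used: 0.30 instead of 0.40 with four visits, 0.32 with five, both for a constant post-operative effect. In that case a chance screening difference also enters the estimate directly, as one of the averaged visits.

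A reader might also infer that the sample size is wrong. It is not: it reproduces from its own inputs and does not rely on baseline adjustment. All figures rest on the assumed correlations, the equal-correlation structure and arms comparable at screening. Severity: should-fix, as a free improvement.

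**What to change.** In section 6.4.1:

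- Use only the post-operative visits as outcomes in the between-arm model for SF-36 and AOFAS.
- Add the patient's own pre-operative score as a covariate, alongside age, gender, BMI and diabetes.
- Name the between-arm contrast and the time point for each score, and correct the AOFAS two-way sentence so that it compares the arms.
- State whether the 3-month survey is among the visits analysed.

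A separate baseline slope for elective and traumatic surgery is optional. The change should be made before outcome data are examined, because it defines the primary analysis. It costs wording and one or two model terms, with no new data, visits or patients. Section 6.5 needs no change on this account.
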